17.11 Interim Monitoring of Primary Efficacy Endpoint

Interim monitoring will be performed of the primary alternative hypothesis that XR-NTX is non-inferior to TAU at 6 months of follow-up, using a non-inferiority risk ratio of $RR = \text{Pr}(\text{suppressed|NTX})/\text{Pr}(\text{suppressed|TAU}) = 0.75$. There will be no interim efficacy monitoring before 1/3 the participants have attained 24 weeks of follow-up and a sample size-re-estimation is performed (see the sample size re-estimation section below). Assuming the re-estimation does not call for a change in sample size (which would have to be ratified by the DSMB and approved by NIDA), we will on every subsequent DSMB meeting perform interim efficacy monitoring. All interim monitoring will use an O’Brien-Fleming-type boundary with information fraction equal to the proportion of the target sample size with primary outcome, and $\alpha = 0.025$, one-tailed.

Before recommending early termination, the DSMB will consider:

- Internal consistency of primary and secondary results.
- Internal consistency of primary and secondary results by subgroups defined by baseline characteristics.
- Distribution of baseline prognostic factors among the two groups.
- Consistency of primary and secondary results across sites and among sites enrolling larger numbers of participants.
- Possible bias in assessment of primary and secondary response variables.
- Possible impact of missing data from missed participant visits for assessment of the primary and secondary response variables.
- Possible differences in concomitant interventions or medications.

[figure not shown]
Sample Size Re-estimation

We plan to also perform a sample size re-estimation after about 1/3 off the total expected number of participants ($n=116$) attain their 24 week outcome, which is approximately 13 months into enrollment. The motivation for sample size re-estimation is that the original sample size calculation was based not only on a hypothesized treatment effect, but also on assumptions about nuisance parameters such as variances and attrition. In the case of CTN-0067, these nuisance parameter estimates are implicitly contained in the Random Assignment Bootstrapping approach we adopted for our sample size calculation, based on pilot data from CTN-0055. It seems reasonable to supplant that calculation with one based on ~100 actual CTN-0067 observations.

The Randomized Assignment part of the Bootstrap approach, when applied to these observations, will automatically suppress the observed treatment effect in favor of one representing the design alternative.

The timing of the sample size re-estimation is based on a number of factors: recruitment rate, timing of primary outcome, and time to perform the sample size re-estimation. For CTN-0067, we use the graphical tool presented in **Figure 7** to assist in assessing the appropriate timing of sample size re-estimation. To illustrate, **Figure 7** shows in a picture the timing of re-estimation when 33% of the participants have outcome data [information fraction = 0.33 (N=116) on the red line] and assuming enrollment (blue line) in CTN-0067 of 350 participants over a 22-month period. This time period to perform the sample size re-estimation corresponds to approximately 13 months after enrollment into CTN-0067 has started, at which point, the study will have enrolled about 60% of the target sample size. If recruitment takes longer or shorter than expected, modifications can be made to the timing of the sample size re-estimation.

17.11.1 Figure 7. Information Fraction and Fraction of Target Enrollment for Proposed Sample Size Re-Estimation Based on Months from Start of Enrollment

17.12 Conditional Power and Futility

Unless otherwise requested, we will perform a futility/conditional power calculation every time we do interim monitoring. If at any DSMB meeting the conditional power falls below 0.3 (when hypothetical future observations are generated under the design alternative $RR=1$ but tested under the null $RR \leq 0.75$), this will stimulate a discussion among the DSMB members about whether we should stop for futility. The conditional power calculation may be carried out via Random Assignment Bootstrapping, similar to the sample-size re-estimation procedure, except that in conditional power, one uses the data already gathered in two ways: first, one includes it in every iteration unchanged as part of the simulated final sample, and second, one Random-

Assignment Bootstraps from it to form the rest of the simulated final sample. In contrast, when one re-estimates the sample size, the entire simulated final sample of each iteration is drawn from the already-gathered sample via Random-Assignment Bootstrapping.

17.13 Safety Analysis

Adverse events (AEs), including serious adverse events (SAEs), will be summarized by body system and preferred term using MedDRA (The Medical Dictionary for Regulatory Activities). Adverse events will be presented in two ways: (1) the number and proportion of participants experiencing at least one incidence of each event will be presented overall and by treatment group; and (2) a table displaying the total number of each event will be given overall and by treatment group. Listings of serious adverse events will be given, sorted by treatment, body system, and preferred term. Detail in these listings will include severity, relationship to study drug, and action taken as available. Treatment arm differences will be monitored by the DSMB.

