15.2 Non-Fatal Overdose

Non-fatal opioid overdoses in the past 4 weeks will be assessed using a self-reported instrument used in previous studies at baseline and 24 weeks (or the end of study visit, if not week 24) [160]. Overdose events are sentinel events that are less likely to be prone to recall bias than other events. If non-fatal overdose resulted in a serious adverse event, it should also be captured on the AE/SAE CRF.

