15.3 Fatal Overdose

We will collect data on fatal opioid overdoses using medical chart record review at 24 weeks for participants who are lost to follow-up. We will supplement this with information from contacts with persons listed on the participant's locator form when participants are lost to follow-up throughout the study. If a fatal opioid overdose occurred, the event also should be captured on the AE/SAE CRF.

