19.3.2 Serious Adverse Events

For the purpose of this study, the following events will not be reported as an SAE, but will be recorded on study specific forms in the data system.

- 1) Detox admissions (documented instead on the DTX form).**
- 2) Admission for labor and delivery (documented instead on the Confirmed Pregnancy and Outcomes form).**
- 3) Admission for elective or pre-planned surgery.**

The Lead Node will report all other SAEs on the Serious Adverse Event form in the data system. Sites must determine if local IRBs will require annual or other SAE reporting.

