19.4 Known Potential Toxicities of Study Drug/Intervention

Refer to the package insert for XR-NTX.

19.5 Known Potential Adverse Events Related to the Underlying Clinical Condition and/or Study Populations

Each of the participating research sites has established practices for managing medical and psychiatric emergencies, and the study staff will continue to utilize these procedures. Treatment providers at each research site will be responsible for monitoring participants for possible clinical deterioration or other problems, and for implementing appropriate courses of action.

As this population will have significant ongoing health and substance use issues, events related to complications of HIV, substance use treatment or admission for substance detoxification will be captured on study-specific forms and not duplicitely reported as an adverse or serious adverse event. All hospitalizations for other (non-HIV, non-substance-use related) medical, surgical and psychological reasons and deaths will be reported on AE/SAE forms. These data will still be included in the reports to the DSMB at the regular meetings.

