23.1 Definition of Adverse Events and Serious Adverse Events

An **Adverse Event** (AE) is any untoward medical occurrence in humans, whether or not considered study drug/intervention related which occurs during the conduct of a clinical trial. Any change from baseline in clinical status or any findings from lab results, x-rays, physical examinations, etc., that are considered clinically significant by the study medical clinician are considered AEs.

Suspected adverse reaction is any adverse event for which there is a reasonable possibility that the study drug/intervention caused the adverse event. A reasonable possibility implies that there is evidence that the study drug/intervention caused the event.

Adverse reaction is any adverse event caused by the study drug/intervention.

An **adverse event, suspected adverse reaction, or adverse reaction** is considered “**serious**” (i.e., a serious adverse event, serious suspected adverse reaction or serious adverse reaction) if, in the view of either the study medical clinician or sponsor, it:

- 1) Results in death: A death occurring during the study or which comes to the attention of the study staff during the protocol-defined follow-up period, whether or not considered caused by the study drug/intervention, must be reported.
- 2) Is life-threatening: Life-threatening means that the study participant was, in the opinion of the medical clinician or sponsor, at immediate risk of death from the reaction as it occurred and required immediate intervention.
- 3) Requires inpatient hospitalization or prolongation of existing hospitalization.
- 4) Results in persistent or significant incapacity or substantial disruption of the ability to conduct normal life functions. Is a congenital abnormality or birth defect.
- 5) Important medical event that may not result in one of the above outcomes, but may jeopardize the health of the study participant or require medical or surgical intervention to prevent one of the outcomes listed in the above definition of serious event.

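### Section 19.5 can be read to keep non-fatal overdose admissions off the AE/SAE forms, against 15.2 and 19.3.2, and 17.13 plans no once-per-participant overdose count by arm

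*Combined protocol and SAP*

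**What the plan says.** **Analysis.** Section 17.13 states: "Adverse events (AEs), including serious adverse events (SAEs), will be summarized by body system and preferred term using MedDRA". It plans participant counts for each event and total event counts, both by treatment group, plus SAE listings. Overdose is not mentioned.

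**Collection.** Section 15.2 sets up a dedicated form: "Non-fatal opioid overdoses in the past 4 weeks will be assessed using a self-reported instrument used in previous studies at baseline and 24 weeks". Participants who end the study at another time complete it at their final visit. The assessment table in 10.1 does not mark this form as XR-NTX only, so it applies to both arms. Section 15.3 covers fatal overdose. Section 9.1.6 lists overdose among the items abstracted from medical records to corroborate self-report.

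**Reporting.** Four places bear on whether an overdose reaches the AE/SAE form:
- 15.2 (non-fatal): "If non-fatal overdose resulted in a serious adverse event, it should also be captured on the AE/SAE CRF".
- 15.3 (fatal): "If a fatal opioid overdose occurred, the event also should be captured on the AE/SAE CRF".
- 19.3.2 exempts detox admissions, labor and delivery admissions, and elective or pre-planned surgery. It then says: "The Lead Node will report all other SAEs on the Serious Adverse Event form in the data system".
- 19.5 says that "events related to complications of HIV, substance use treatment or admission for substance detoxification will be captured on study-specific forms" and are not reported a second time as AEs or SAEs. It continues: "All hospitalizations for other (non-HIV, non-substance-use related) medical, surgical and psychological reasons and deaths will be reported on AE/SAE forms".

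Section 23.1 in Appendix A lists among the criteria for a serious event: "Requires inpatient hospitalization or prolongation of existing hospitalization".

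**The concern.** The 17.13 tables draw on AE/SAE records alone. If sites differ on whether a non-fatal overdose admission belongs on the AE/SAE form, the by-arm tables will differ by site for a reason unrelated to treatment. The one form designed to ask every participant about overdose cannot repair this, because no analysis uses it.

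This matters because of the event. Section 24.2.5.5 lists opioid intoxication after a missed XR-NTX dose, or at the end of a dosing interval, as a potentially life-threatening study-specific risk. Section 4.1 cites criticism that the approval trial did not adequately assess post-treatment overdose. A reader of a non-inferiority result on viral suppression would want one overdose figure per arm beside it. The trial is also unblinded (9.7), so the case definition and the way sources are combined are better fixed in advance.

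**Working it through.** No stated figure is in dispute, so the main check sets the rules side by side.

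**Step 1. A participant is admitted with a non-fatal opioid overdose.**

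| Rule | AE/SAE form? |
|---|---|
| 23.1: inpatient stay is serious | Event is an SAE |
| 15.2 | Yes, in addition to the overdose form |
| 19.3.2: not one of the three exemptions | Yes |
| 19.5, literal: the admission is substance-use-related | Not among the hospitalizations sent to the form |
| 19.5, narrow: "other" means other than the events just listed, and overdose is not listed | Yes |

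Only the literal reading of 19.5 produces a conflict, but the wording allows it.

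**Step 2. Other overdoses.** Fatal overdoses are reportable under 15.3, 19.3.2 and 19.5 alike. Non-fatal overdoses without admission should mostly reach the tables as AEs. AEs are solicited at each visit (15.1) and collected from consent to 30 days after the last study visit (23.4). They stay out of the data system only if both mild and unrelated (19.3.1).

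**Step 3. Where the overdose form is analysed.** Overdose is absent from the outcome lists in 8.2 and 17.3, from the analyses in 17.9 and 17.9.1, and from 17.13. The participant count in 17.13 is made separately for each event. No pooled row exists, and the plan does not say which terms would count as overdose.

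**Step 4. Illustrations.** The documents supply n = 175 per arm, a 24-week period and a 4-week recall window. The 24-week overdose risk p and the missed share m are assumptions.

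*Could the scheduled form stand alone?* Its window covers 4/24 = 16.7% of follow-up. With constant hazard h = −ln(1−p)/24, the 4-week risk is 1 − exp(−4h):

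| Assumed p | Participants with overdose, 175p | 4-week risk | Expected in window, of 175 |
|---|---|---|---|
| 3% | 5.25 | 0.506% | 0.89 |
| 5% | 8.75 | 0.851% | 1.49 |
| 10% | 17.5 | 1.741% | 3.05 |

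It could not. The form can add to AE records but not replace them. If it is also completed as needed, these figures are lower bounds.

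*How much might the AE/SAE tables miss?* Missed per arm = 175 × p × m. With m from 0 to 0.25, the result is 0 to 2.2 of 8.75 at p = 5%, and 0 to 4.4 of 17.5 at p = 10%.

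*How precise would a pooled row be?* Newcombe 95% limits for the risk difference, with equal events in two arms of 175, are ±4.00 points (5 v 5), ±4.97 (9 v 9) and ±6.52 (18 v 18). These counts are 175p at 3%, 5% and 10%, rounded to whole events (2.9%, 5.1% and 10.3%).

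**The case against.** The strongest reply is that 17.13 already does most of the work. Overdoses that sites know of enter as AEs, those that are SAEs are directed to the AE/SAE form by name, and by-arm counts and listings follow. On this view a pooled row only improves presentation. Section 15.2 names overdose, and a specific instruction should govern a general one such as 19.5. Section 19.5 adds that its data still go into DSMB reports, and 17.13 has the DSMB monitor differences between arms. Chart data collected to corroborate self-report need no analysis of their own.

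Much of this stands. A reader might infer that overdose is missing from the safety analysis, or that 19.5 forbids reporting it. The documents support neither: most overdoses known to sites have a route into the tables, and 19.5 can be read consistently with 15.2. Nor does the point suggest that the DSMB would be uninformed.

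Two things survive. Choosing between readings is left to each site, and one reading drops an event that the other sections require. DSMB monitoring is also not a specified final analysis, so the plan still does not yield a count of participants with any overdose by arm.

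**Conclusion.** The point holds in a limited form and is worth fixing before the data are analysed. Section 19.5 permits a reading that conflicts with 15.2 and 19.3.2 for non-fatal overdose admissions. The both-arm overdose form has no planned by-arm analysis, and 17.13 has no once-per-participant count for a risk the protocol itself names.

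The size of any under-count cannot be derived from the documents. The illustrated ranges rest wholly on assumed risks and an assumed missed share, and they include zero. They are not evidence that events will be lost.

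A reader might also infer from 9.1.6 that overdoses are ascertained from charts to week 52, leaving a long period covered by charts only. The text does not establish that. The 52-week limit may describe when record review can be carried out rather than how long events are sought, so no chart-only period is claimed here.

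The primary non-inferiority conclusion is unaffected.

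**What to change.** 1. In 19.5, state that non-fatal overdose admissions are reported on the AE/SAE form, as 15.2 and 19.3.2 require.
2. In 17.13, add one descriptive row: number and proportion of all randomized participants with any opioid overdose, fatal or non-fatal, from randomization through week 24, by randomized arm. Combine the two overdose forms, AE/SAE records and chart abstraction, count each event once, and define which terms qualify. Give a risk difference with 95% CI, without multiplicity control.
3. Add a separate listing of later chart events only if 9.1.6 is confirmed to ascertain overdoses through week 52.

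The cost is one sentence, one paragraph with its table row, and a de-duplication rule. No new visits, forms or participants are needed. The downside is one more low-precision comparison that could be over-read, so the row should be labelled descriptive.

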- 2) **Patient Acceptability.** Patients were interested in XR-NTX treatment, as well. The study site in Vancouver, B.C. conducted a survey of 657 persons who inject opioids as part of their site selection application. About half (52%) of the survey participants expressed willingness to receive XR-NTX treatment for opioid use disorder. Daily heroin injection was associated with increased willingness to try XR-NTX (OR 1.53, 95% CI 1.02, 3.12) [107]. Prospective CTN-0055 CHOICES pilot study participants (n=112) were asked about their willingness to participate in a trial of XR-NTX during pre-screening. Ninety-eight percent of prospective participants interested in reducing opioid use (n=60) and 99% of those interested in reducing alcohol use (n=82) were definitely or maybe willing to consider enrolling in a clinical trial of XR-NTX.
- 3) **Randomization Rate.** The CTN-0055 CHOICES pilot study enrolled 51 HIV-infected patients receiving care at two pilot site HIV clinics (mean age 46 years, mean CD4 count 620; 43% women). The trial achieved 155% actual versus expected randomizations, reaching randomization targets 4 months ahead of schedule and enrolling 22 (43%) participants with opioid and 29 (57%) with alcohol as their primary use disorder. Sixteen percent of randomized participants met criteria for *both* opioid and alcohol use disorders. Overall, the pilot study enrolled a mean of 3 participants per month per site.
- 4) **Treatment Initiation.** The majority (68%) of participants assigned to XR-NTX initiated treatment. Five of 12 (42%) participants with any OUD assigned to XR-NTX initiated XR-NTX within 4 weeks of randomization. The CTN-0055 CHOICES pilot study randomized participants prior to detoxification and provides the first benchmark for XR-NTX treatment initiation in community-dwelling people with opioid use disorder. Both of the two clinical trials of XR-NTX for opioid use disorder that led to FDA approval required successful residential detoxification prior to randomization and did not report treatment initiation rates [54, 55]. The CTN-0067 scale-up trial seeks to increase the rate of treatment initiation for participants with OUD with a modified naltrexone induction protocol (Section 9.2.3.1).

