9.1.9 Randomization

The timing of randomization will follow shortly after baseline assessments and final confirmation of eligibility. Participants will be encouraged to initiate treatment within 28 days of randomization. If a participant is unable to initiate treatment within 28 days, he or she may initiate XR-NTX study drug at any time until week 20 and may initiate TAU at any time during the trial. Initiation of assigned treatment will be tracked.

Participants will be randomized in a 1:1 fashion to either office-based XR-NTX or TAU using a permuted block design with randomly-sized blocks. Randomization will be stratified only by site. Participants who meet DSM-5 criteria for both opioid and alcohol use disorder (16% of CTN-0055 CHOICES pilot study participants) will be included, in addition to participants with OUD, alone.

Concomitant alcohol use disorder will be considered as a potential covariate [31], [127, 128]. Participants need not be abstinent from opioids at the time of randomization.

The randomization procedure will be conducted in a centralized process through the Data and Statistics Center (DSC). Specifically, randomization schedules will be created by the study statistician for each site. The randomization schedules will be of a randomized-block nature to ensure relative equality of assignment across condition across the recruitment period and to prevent the potential for study staff guessing the next assignment, which is heightened when a fixed block-size is used. After the baseline assessment is successfully completed, a designated site study staff member will perform the randomization. Randomization for each participant is done over the internet using the Enrollment Module in Advantage eClinical.

The DSC statistician will review the randomization data on a regular basis to ensure that the scheme is being implemented according to plan. If a participant drops out of the study at any point after randomization, the randomization slot will not be re-allocated to a new participant due to the intent-to-treat nature of the study.

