15.4 Precipitated Withdrawal

For participants assigned to XR-NTX, the study clinician will record the presence or absence of precipitated opioid withdrawal on the XR-NTX Administration (INJ) CRF following each XR-NTX injection.

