17.0 STATISTICAL ANALYSIS

17.1 Primary Objective of the Analysis

The Primary objective of the CTN-0067 CHOICES scale-up study is to discover whether HIV clinic-based XR-NTX is non-inferior to TAU with respect to HIV viral suppression in HIV-infected participants with opioid use disorder. We have chosen a non-inferiority margin of 0.75. That is, we will reject the null hypothesis of inferiority of XR-NTX to TAU in favor of non-inferiority if the lower 95% confidence limit for the ratio $\frac{\text{Pr}(\text{suppressed}|\text{NTX})}{\text{Pr}(\text{suppressed}|\text{TAU})}$ is strictly greater than 0.75. We anticipate a sample size of 350 (175/arm) will grant at least 80% power for the non-inferiority conclusion.

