23.4 Site's Role in Eliciting and Reporting Adverse Events

Appropriately qualified and trained study staff will elicit participant reporting of AEs and SAEs at each study visit designated to collect AEs. Adverse events (medical and/or psychiatric) assessment will initiate with participant consent and follow-up will continue through 30 days post last study visit. Study staff will obtain as much information as possible about the reported AE/SAE to complete the AE/SAE forms and will consult with the lead team as warranted.

Standard reporting, within 7 days of the site becoming aware of the event, is required for reportable AEs. Expedited reporting (within 24 hours of their occurrence and/or site's knowledge of the event) is required for reportable SAEs (including death and life-threatening events). Local sites are responsible for reporting SAEs to their IRB, per their IRB's guidelines when operating under an IRB Authorization Agreement.

Site staff is required to enter reportable AEs and SAEs in the Advantage eClinical system. The AE form is used to capture reportable AEs (as defined in the protocol). Additional information may need to be gathered to evaluate serious adverse events and to complete the appropriate CRFs and the summary. This process may include obtaining hospital discharge reports, medical records, autopsy records or any other type of records or information necessary to provide a complete and clear picture of the SAE as well as events preceding and following the SAE. If the SAE is not resolved or stable at the time of the initial report or if new information becomes available after the initial report, follow-up information must be submitted as soon as possible.

Reportable adverse events will be followed until resolution, stabilization or study end. Any serious adverse reactions will be followed until resolution or stabilization even beyond the end of the study.

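### Section 17.13 plans no safety table for participants who actually received XR-NTX, so the risk of harms that need an injection would be shown diluted by the share injected

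*Combined protocol and SAP*

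**What the plan says.** Section 17.13 plans two adverse event tables. In the first, "the number and proportion of participants experiencing at least one incidence of each event will be presented overall and by treatment group"; in the second, "a table displaying the total number of each event will be given overall and by treatment group". SAE listings are sorted by treatment and show relationship to study drug where available. The section closes with "Treatment arm differences will be monitored by the DSMB". It does not define treatment group, a safety population, a rule for participants never injected, a split at first injection, or any rate based on exposure.

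Exposure is delayed and uncertain by design. Section 9.2.3.1 places detoxification and induction after randomization. For participants who cannot start within 28 days, section 9.1.9 says "he or she may initiate XR-NTX study drug at any time until week 20 and may initiate TAU at any time during the trial". On the pilot, section 4.3 reports: "Five of 12 (42%) participants with any OUD assigned to XR-NTX initiated XR-NTX within 4 weeks of randomization". It also gives 68% initiation across all pilot participants assigned to XR-NTX, and says the induction protocol has been modified to raise initiation; no target rate is stated.

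On collection of events, section 23.4 says that "assessment will initiate with participant consent and follow-up will continue through 30 days post last study visit". Section 24.2.1 instead ends collection 30 days after the last active treatment visit. Under section 15.4, "the study clinician will record the presence or absence of precipitated opioid withdrawal on the XR-NTX Administration (INJ) CRF following each XR-NTX injection".

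**The concern.** A clinic deciding whether to offer XR-NTX will ask how often people who receive the injection are harmed by it. Section 4.1 says that the Russian efficacy trial does not directly address XR-NTX safety in U.S. HIV-infected populations, and presents CHOICES as the first study in an HIV clinic population, so readers will look here for that answer. A table by randomized arm answers a different question: what happens to people assigned to the XR-NTX strategy, whether or not they are injected. When a sizeable share of the arm is never injected or starts late, the two answers can differ a good deal.

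Section 17.10 does plan analyses by treatment received and among those with at least one dose. They appear where the plan deals with suppression and missing data, and 17.13 does not take them up for safety. The study-specific risk named in section 24.2.5.5, overdose late in a dosing interval or after a missed dose, depends on time since injection, and no table in 17.13 relates events to injections.

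**Working it through.** **Inputs from the documents.** XR-NTX arm size 175 (17.1). Pilot initiation within 4 weeks among participants with opioid use disorder: 5 of 12 (4.3). Pilot initiation overall: 68% (4.3). Latest first injection: week 20 of 24 (9.1.9). The documents give no harm risks, so every risk below is an assumption.

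**1. The plan's pilot figure.** 5/12 = 41.7%, which rounds to the stated 42%. The exact (Clopper-Pearson) 95% interval is 15.2% to 72.3%.

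**2. Applied to the arm.** 175 × 5/12 = 72.9, about 73 injected by week 4 and 102 not. At 68%: 175 × 0.68 = 119 injected and 56 not.

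**3. Dilution.** Let q be the share injected, r1 the risk in the injected and r0 the risk in the non-injected. The by-arm proportion is q × r1 + (1 − q) × r0.

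For a harm that needs an injection, r0 = 0 and the by-arm figure is q × r1. With r1 = 10% (assumed):

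| Share injected q | Shown by arm |
|---|---|
| 15.2% (lower CI limit) | 1.5% |
| 41.7% (5/12) | 4.2% |
| 68% | 6.8% |
| 72.3% (upper CI limit) | 7.2% |

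**4. Harms that also occur without an injection**, at q = 5/12:
- r1 = 20%, r0 = 5% (assumed): 0.417 × 0.20 + 0.583 × 0.05 = 11.3%, which is 0.56 times the risk in the injected.
- r1 = 5%, r0 = 10% (assumed): 0.417 × 0.05 + 0.583 × 0.10 = 7.9%, which is 1.58 times the risk in the injected.

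So for these harms the by-arm figure may lie on either side of the risk in the injected.

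**5. Late starts.** The share of the 24 weeks left after a first injection at week 4, 12 or 20 is 20/24 = 83%, 12/24 = 50% and 4/24 = 17%. A count of injected participants alone would therefore still mix very different exposure times, which is why a person-time rate is needed.

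**The case against.** The by-arm table is a valid randomized comparison. Detoxification and induction belong to the assigned XR-NTX strategy, so harms arising there are properly counted in that comparison. This stands, and the table should be kept.

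The wording is treatment group, not randomized arm. This also stands: randomized arm is an inference, though the natural one given the closing sentence of 17.13 and the intention-to-treat rule in 17.10. The term needs defining either way.

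The initiation shares are weak evidence for this trial. The 42% rests on 12 people and counts only starts within 4 weeks; later starts would raise the share ever injected, and induction has been modified. The 68% includes participants with alcohol use disorder only. The pilot account does not separate never-injected participants from late starters. So the size is illustrative, but the gap in 17.13 does not depend on it.

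A reader might also infer that by-arm tables will be swamped by detoxification events. The documents do not support that: sections 19.3.2 and 19.5 send detoxification admissions, and events related to HIV complications or substance use treatment, to study-specific forms rather than AE or SAE reports. Nor do events before randomization bias the comparison of arms. Randomization balances them in expectation, so they add noise, and section 10.1 schedules AE assessment only from baseline.

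Finally, the missing tables could be built later from data already collected, so nothing is irretrievably lost. That limits the severity. It does not replace naming the tables in advance.

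**Conclusion.** The point holds in a limited form. As written, 17.13 would not show the risk of harm among people who received XR-NTX. For injection-dependent harms that reach the AE tables, such as injection-site reactions, the by-arm proportion is the true risk times the share injected: 4.2% or 6.8% for an assumed 10% risk at 42% or 68% injected. This rests on treatment group meaning randomized arm and on the harm not occurring without an injection.

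A reader might infer that XR-NTX harms in general will be understated. The documents do not support that. For overdose, hepatic events and other harms that also occur without an injection, the direction depends on the risk in the non-injected, which is unknown, and the by-arm figure could overstate the risk in the injected. A reader might also infer that precipitated withdrawal is divided by the whole arm. It is not: it is recorded after each injection, and the gap is that 17.13 names no summary of it.

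This is an inexpensive improvement to the safety reporting, not a flaw in the randomized comparison.

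**What to change.** In section 17.13:

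1. State that treatment group means randomized arm. Keep those tables as the between-arm comparison, limited to events with onset after randomization.
2. Add a table, labelled descriptive and non-randomized, for participants with at least one XR-NTX injection. Split events before and after first injection, and give rates per person-time after first injection.
3. Report precipitated withdrawal and injection-site events per injected participant and per injection.
4. Reconcile the two stated ends of AE collection (sections 23.4 and 24.2.1), so that the window for these tables is defined.

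The cost is SAP wording and a few extra tables. Section 12.10 already records participants who are never injected. Section 10.1 marks the XR-NTX Administration Log, but not the XR-NTX Injection entry, as not captured in eClinical, so the sponsor should confirm that injection dates and the withdrawal item are in the database. The downside is that participants who get as far as an injection are a selected group, so the added table must not be read as a comparison with TAU.
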